6.3.1 Decimal Places

Derived data where it is known in advance the result will be an integer for example, such as age, will be presented with zero decimal places.

Mean and median will be displayed to one more decimal place than the data, standard deviation will have two more decimal places, and the minimum and maximum will be displayed to the same number of decimal places as reported in the raw data. Percentages will be displayed with one decimal place.

For PK data, individual concentrations and PK parameters will be reported to 3 significant figures. For summary statistics, n will be reported as a whole number; mean, SD, median, min, max, geometric mean, CV%, and geometric CV% will be reported to the same precision as for individual

QMD Ref: Worldwide-TMP-ST-006-4.0 Effective: 12Aug2019	Governing QMD: Worldwide-SOP-ST-001
Confidentiality Statement	
This document is the property of Worldwide Clinical Trials Inc. and may not be duplicated, copied, altered or removed from company without prior approval from Worldwide Quality Assurance or in compliance with Worldwide Standard Operating Procedures.	

Worldwide Clinical Trials Controlled Quality Management Document		
 WORLDWIDE CLINICAL TRIALS	Sponsor: Protocol Number:	Opiant Pharmaceuticals OPNT003-PK-002

data. p-values will be reported to 4 decimal places. Percent ratios of the geometric least squares means and associated 90% confidence intervals will be reported to 2 decimal places. Time will be presented to 3 significant figures.

6.4 Subject Disposition

Subject disposition will be summarized for all randomized subjects as follows:

- The number of subjects who were randomized; number and percentage of subjects in each analysis population will be summarized by treatment sequence and overall.
- The number and percentage of subjects who completed the study and who terminated early, along reason for early termination, will be summarized based on the Safety Population.

The Safety and PK Evaluation Population will be based on actual treatment received. Percentage for safety population will be based on randomized subjects. Percentages for all other categories will be based on Safety Population. Percentage for “Reason for withdrawal” is based on number of non-completers.

A listing of population flags, disposition details and reason for exclusion from population will be provided.

In Mock Shells: Table 14.1.1.1, Listing 16.2.1.1, Listing 16.2.3.1.

6.5 Protocol Deviations

A listing of protocol deviations will be provided within Appendix 16.2 of the CSR.

In Mock Shells: Listing 16.2.2.1.

6.6 Demographics and Baseline Comparability

Subject demographics will be summarized by treatment sequence and overall. Categorical and continuous variables will be provided in the same table. The following variables will be presented: age at Informed Consent (years), sex, ethnicity, race, baseline height (cm), baseline weight (kg), baseline BMI (kg/m^2). Percentages will be based on the respective population.

The summaries will be repeated for Safety and PK Evaluation Populations (as per ICH E3 Guidelines). If the populations are the same, then demographic summary for PK Evaluable Population will be removed.

A listing of subject demographics, baseline characteristics and contraception details will be provided.

In Mock Shells: Table 14.1.2.1 to 14.1.2.2, Listing 16.2.4.1.

QMD Ref: Worldwide-TMP-ST-006-4.0 Effective: 12Aug2019	Governing QMD: Worldwide-SOP-ST-001
Confidentiality Statement	
This document is the property of Worldwide Clinical Trials Inc. and may not be duplicated, copied, altered or removed from company without prior approval from Worldwide Quality Assurance or in compliance with Worldwide Standard Operating Procedures.	

Worldwide Clinical Trials Controlled Quality Management Document		
 WORLDWIDE CLINICAL TRIALS	Sponsor:	Opiant Pharmaceuticals

6.7 Medical History

Previous and ongoing conditions at screening will be listed for the Safety Population. Conditions will be coded using the Medical Dictionary of Regulated Activities (MedDRA, version 24.1 or higher) and primary SOC and PT will be presented in listings.

In Mock Shells: Listing 16.2.4.2.

Prior conditions are defined as all conditions starting and stopping before the date of first dose of study drug. Ongoing conditions are defined as conditions present on or after the date of first dose of study drug.

6.8 Prior and Concomitant Medications

Prior and concomitant medications will be listed for the Safety Population. Medications will be coded using the WHO Drug Dictionary (version Sep 2021 or later). Prior medications are defined as all medications that ended before the date of first dose of study drug. Concomitant medications are defined as medications ongoing on or after the date of first dose of study drug.

In Mock Shells: Listing 16.2.4.3.

6.9 Exposure to Study Drug

All dosing information will be listed.

In Mock Shells: Listing 16.2.5.1.

6.10 Pharmacokinetic Analyses

The dose-normalized pharmacokinetic parameters C_{max} , AUC_{inf} , $AUC_{0-2.5\text{ mins}}$, $AUC_{0-5\text{ mins}}$, $AUC_{0-7.5\text{ mins}}$, $AUC_{0-10\text{ mins}}$, $AUC_{0-15\text{ mins}}$, $AUC_{0-20\text{ mins}}$ and $AUC_{0-30\text{ mins}}$ for nalmefene will be compared between the treatments using an analysis of variance (ANOVA) model with treatment, period, sequence, and subject within sequence as the factors using the natural logarithms (ln) of the dose-normalized parameters. The following comparisons will be made:

- 6 mg IN (2 x 3 mg in one nostril; T3, Treatment C) vs. 3 mg IN (in one nostril; T1, Treatment A)
- 6 mg IN (3 mg in each nostril; T2, Treatment B) vs. 3 mg IN (in one nostril; T1, Treatment A)
- 6 mg IN (3 mg in each nostril; T2, Treatment B) vs. 6 mg IN (2 x 3 mg in one nostril; T3, Treatment C)

Confidence intervals (CI) (90%) will be constructed for the geometric mean ratios, using the log-transformed data and the two one-sided t-tests procedure. The point estimates and confidence

QMD Ref: Worldwide-TMP-ST-006-4.0 Effective: 12Aug2019	Governing QMD: Worldwide-SOP-ST-001
Confidentiality Statement	

This document is the property of Worldwide Clinical Trials Inc. and may not be duplicated, copied, altered or removed from company without prior approval from Worldwide Quality Assurance or in compliance with Worldwide Standard Operating Procedures.

Worldwide Clinical Trials Controlled Quality Management Document		
 WORLDWIDE CLINICAL TRIALS	Sponsor: Protocol Number:	Opiant Pharmaceuticals OPNT003-PK-002

limits will be exponentiated back to the original scale. Comparability between the nalmefene intranasal 2 sprays and nalmefene intranasal 1 spray will be assessed from the geometric mean ratios and 90% CIs. All three will be included in the same ANOVA model will separate contrasts defined for each comparison.

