6.1.2 Pharmacokinetic Evaluation Population

Pharmacokinetic Analysis Population for Test 2 versus Test 1 Comparison (B vs. A)

The pharmacokinetic analysis population for Test 2 versus Test 1 comparison will include all subjects who have evaluable pharmacokinetic data on the Test 2 period and on the Test 1 period and did not deviate from the protocol in a way that might affect the evaluation of the pharmacokinetic endpoints.

Pharmacokinetic Analysis Population for Test 3 versus Test 1 Comparison (C vs. A)

The pharmacokinetic analysis population for Test 3 versus Test 1 comparison will include all subjects who have evaluable pharmacokinetic data on the Test 3 period and on the Test 1 period and did not deviate from the protocol in a way that might affect the evaluation of the pharmacokinetic endpoints.

Pharmacokinetic Analysis Population for Test 2 versus Test 3 Comparison (B vs. C)

QMD Ref: Worldwide-TMP-ST-006-4.0 Effective: 12Aug2019	Governing QMD: Worldwide-SOP-ST-001
Confidentiality Statement	
This document is the property of Worldwide Clinical Trials Inc. and may not be duplicated, copied, altered or removed from company without prior approval from Worldwide Quality Assurance or in compliance with Worldwide Standard Operating Procedures.	

Worldwide Clinical Trials Controlled Quality Management Document		
 WORLDWIDE CLINICAL TRIALS	Sponsor:	Opiant Pharmaceuticals

The pharmacokinetic analysis population for Test 2 versus Test 3 comparison will include all subjects who have evaluable pharmacokinetic data on the Test 2 period and on the Test 3 period and did not deviate from the protocol in a way that might affect the evaluation of the pharmacokinetic endpoints.

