If K_{el} acceptance criteria are met and AUC_{inf} is estimable, the following criteria are used to report AUC_{inf} :

- The percentage of AUC_{inf} based on extrapolation should be $<30.0\%$.

If the percentage of AUC_{inf} based on extrapolation is 30.0% or greater, AUC_{inf} and $AUC_{\%extrap}$ will be excluded from summary statistics, subsequent PK calculations (e.g. CL/F, V_z/F), and statistical analysis (e.g. ANOVA).

Individual PK parameters will be listed by treatment and summarized by descriptive statistics: n, mean, SD, median, min, max, CV%, geometric mean, and geometric CV%.

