7 CHANGES TO PLANNED PROTOCOL ANALYSIS

During the analysis and reporting process, any deviations from the statistical analysis plan will be described and justified in writing in the CSR.

QMD Ref: Worldwide-TMP-ST-006-4.0 Effective: 12Aug2019	Governing QMD: Worldwide-SOP-ST-001
Confidentiality Statement This document is the property of Worldwide Clinical Trials Inc. and may not be duplicated, copied, altered or removed from company without prior approval from Worldwide Quality Assurance or in compliance with Worldwide Standard Operating Procedures.	

Worldwide Clinical Trials Controlled Quality Management Document		
 WORLDWIDE CLINICAL TRIALS	Sponsor:	Opiant Pharmaceuticals
	Protocol Number:	OPNT003-PK-002

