14.3.7	Concomitant Medication		
	Not Applicable		
14.4	PK Tables		
14.4.1	Descriptive Statistics for Concentration-Time Data of Nalmefene after IN Administration of 3 mg Nalmefene HCl in One Nostril (T1, Treatment A), 3 mg (6 mg Total Dose) Nalmefene HCl in Each Nostril (Treatment B, T2), and 6 mg Nalmefene HCl in One Nostril (Treatment C, T3) – PK Evaluation Population	IP	-
14.4.2	Plasma PK Parameters of Nalmefene after IN Administration of 3 mg Nalmefene HCl in One Nostril (T1, Treatment A), 3 mg (6 mg Total Dose) Nalmefene HCl in Each Nostril (Treatment B, T2), and 6 mg Nalmefene HCl in One Nostril (Treatment C, T3) – PK Evaluation Population	IP	-
14.4.3	Plasma PK Partial AUCs of Nalmefene after IN Administration of 3 mg Nalmefene HCl in One Nostril (T1, Treatment A), 3 mg (6 mg Total Dose) Nalmefene HCl in Each Nostril (Treatment B, T2), and 6 mg Nalmefene HCl in One Nostril (Treatment C, T3) – PK Population	IP	-
14.4.4	Plasma Dose-Normalized Parameters of Nalmefene after IN Administration of 3 mg Nalmefene HCl in One Nostril (T1, Treatment A), 3 mg (6 mg Total Dose) Nalmefene HCl in Each Nostril (Treatment B, T2), and 6 mg Nalmefene HCl in One Nostril (Treatment C, T3) – PK Population	IP	-
14.4.5	Dose-Normalized Plasma PK Partial AUCs of Nalmefene after IN Administration of 3 mg Nalmefene	IP	-

QMD Ref: Worldwide-TMP-ST-006-4.0 Effective: 12Aug2019	Governing QMD: Worldwide-SOP-ST-001
Confidentiality Statement	

This document is the property of Worldwide Clinical Trials Inc. and may not be duplicated, copied, altered or removed from company without prior approval from Worldwide Quality Assurance or in compliance with Worldwide Standard Operating Procedures.

Worldwide Clinical Trials Controlled Quality Management Document			
 WORLDWIDE CLINICAL TRIALS	Sponsor:	Opiant Pharmaceuticals	
	Protocol Number:	OPNT003-PK-002	

Table Number	Table Title	Validation Method	Shell Number (if repeat)
	HCl in One Nostril (T1, Treatment A), 3 mg (6 mg Total Dose) Nalmefene HCl in Each Nostril (Treatment B, T2), and 6 mg Nalmefene HCl in One Nostril (Treatment C, T3) – PK Population		
14.4.6	Statistical Analysis of the Natural Log-Transformed, Dose-Normalized Exposure Parameters of Nalmefene Comparing 6 mg Nalmefene Hydrochloride in One Nostril (Treatment C, T3, Test) and 3 mg Nalmefene Hydrochloride in One Nostril (Treatment A, T1, Reference) – PK Evaluation Population	IP	-

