1. BACKGROUND

This document details changes and / or additions to the planned statistical analyses for Opiant Pharmaceuticals, protocol “OPNT003-PK-002” study previously described in V1.0 of the Statistical Analysis Plan (SAP) dated 16-NOV-2021.

These amendments were made post database lock.

Rationale for Addendum:

- 1) In electrocardiogram assessments, results were summarized only by sequence. Since the data is collected during treatment periods, tables are updated to present results by both treatment and sequence.
- 2) Truncated mean, all subject, and individual subject plots through 4 hours postdose were added to illustrate early nalmefene exposure.

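### Do the three pair-specific PK populations in SAP 6.1.2 conflict with the single ANOVA in SAP 6.10?

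*SAP*

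**What the plan says.** SAP 6.1.2 has a singular heading, Pharmacokinetic Evaluation Population, but defines three sets. The B versus A set "will include all subjects who have evaluable pharmacokinetic data on the Test 2 period and on the Test 1 period"; the C versus A set "will include all subjects who have evaluable pharmacokinetic data on the Test 3 period and on the Test 1 period"; the B versus C set "will include all subjects who have evaluable pharmacokinetic data on the Test 2 period and on the Test 3 period". Each also excludes subjects with deviations that could affect the PK endpoints.

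SAP 6.10 specifies an ANOVA on log dose-normalized parameters with treatment, period, sequence and subject within sequence. It lists the three comparisons and closes with "All three will be included in the same ANOVA model will separate contrasts defined for each comparison" (the second 'will' is evidently a slip for 'with'). It names no population.

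SAP 6.2.10.2 removes an AUCinf value from the ANOVA when 30.0% or more of it is extrapolated.

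In SAP 9, Tables 14.4.1, 14.4.2 and 14.4.6 to 14.4.8 and Listing 16.2.6.4 carry the label PK Evaluation Population. The titles of Tables 14.4.3 to 14.4.5 end "6 mg Nalmefene HCl in One Nostril (Treatment C, T3) – PK Population".

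The addendum says of itself "These amendments were made post database lock". It alters neither 6.1.2 nor 6.10. SAP 7 promises that "any deviations from the statistical analysis plan will be described and justified in writing in the CSR".

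**The concern.** One model needs one data set, and 6.1.2 offers three. Take a subject evaluable for A and B only. The B versus A definition includes this subject and the other two definitions exclude them. If the subject stays in a joint fit, their data help estimate the period effects and the residual variance, and carry weight in the C versus A and B versus C contrasts. If the subject is dropped, the B versus A definition is broken. Read strictly, no single data set meets all three definitions.

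The situation is foreseeable, since SAP 4 enrols 24 to allow for dropouts when 18 completers are wanted. These contrasts serve the primary objective. A rule that is not written down could be chosen with the data in hand, and estimates, error degrees of freedom and intervals would depend on it. The two population labels in the table titles add to the impression that the analysis set was never settled.

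**Working it through.** **When the two sections disagree.** A subject with three evaluable periods is in all three pair sets, so nothing conflicts. A subject with one evaluable period is in none. With subject as a fixed effect, that subject would carry no weight in any contrast anyway. Only a subject with exactly two evaluable periods raises the question.

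**Inputs.** 24 subjects, six sequences, four per sequence (SAP 5). Model factors from SAP 6.10, with subject taken as fixed, which absorbs sequence. CV 10% from SAP 4, taken here as within-subject because it is described as an ANOVA CV. The SAP gives no dropout rate and no CV for Cmax or the partial AUCs, so the missing-data patterns and a 40% CV are assumptions.

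**Formulas.** SE of a log-ratio in units of the within-subject SD: sqrt(c'(X'X)⁻c). Error df = rows − rank of X. Within-subject SD: s = sqrt(ln(1 + CV²)), which is 0.0998 at 10% and 0.385 at 40%. The 90% CI is the ratio divided and multiplied by F = exp(t(0.95, df) × SE × s).

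**Complete data.** The SAP states no SE or interval width to reproduce. With 72 values, rank = 24 + 2 + 2 = 28, so df = 44 and SE = sqrt(2/24) = 0.2887.

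**Patterns.** (i) One sequence 1 subject misses Period 3 (C versus A and B versus C). (ii) One subject per sequence, six in all, misses Period 3 (all contrasts). (iii) One subject per sequence, six in all, has no evaluable Treatment A period (B versus A and C versus A). Cells give SE (df).

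| Pattern | One model, all evaluable periods | Pair set, three-treatment fit | Pair set, two-treatment fit |
|---|---|---|---|
| (i) | 0.2936 (43) | 0.2952 (42) | 0.2955 (20) |
| (ii) | 0.309 (38) | 0.316 (34) | 0.316 (17) |
| (iii) | 0.323 (38) | 0.333 (32) | 0.333 (15) |

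Example, pattern (i), CV 10%:
- One model: exp(1.681 × 0.2936 × 0.0998) = 1.0505.
- Pair set, three treatments: exp(1.682 × 0.2952 × 0.0998) = 1.0508.
- Pair set, two treatments: exp(1.725 × 0.2955 × 0.0998) = 1.0521.

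| Pattern | F at CV 10%: one model / pair sets | F at CV 40%: one model / pair sets |
|---|---|---|
| (i) | 1.0505 / 1.0508–1.0521 | 1.209 / 1.211–1.217 |
| (ii) | 1.053 / 1.055–1.056 | 1.222 / 1.229–1.236 |
| (iii) | 1.056 / 1.058–1.060 | 1.233 / 1.243–1.253 |

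At 10% the largest change in F is 1.060 − 1.056 = 0.004.

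**Gap between point estimates.** The one-model estimate is the efficient one, so the SD of the difference is sqrt(SE_pair² − SE_one²) × s, using the three-treatment fit. Pattern (i) at 10%: sqrt(0.2952² − 0.2936²) × 0.0998 = 0.003, or 0.3%. Patterns (ii) and (iii) give 0.7% and 0.8%. At 40% the three gaps are 1.2%, 2.7% and 3.2%. For scale, the standard error itself in pattern (iii) is 0.323 × 0.0998 = 3.2% at a 10% CV and 0.323 × 0.385 = 12.4% at 40%.

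**The case for a change.** The best case for a change is that these are primary comparisons, that the choice would fall after database lock, and that the 10% CV rests on AUCinf alone while the same model serves Cmax and seven early partial AUCs. In one simulated data set with an assumed CV of 25% and three subjects evaluable for A and B only, the upper limit for B versus A was 124.51 from the single model and 125.01 from a fit to those two treatments alone, on either side of 125.00.

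That example does not show a population conflict. All 24 subjects are in the B versus A set under both fits, and both give a ratio of 110.50. The three-treatment model on the B versus A set returns 98.07 to 124.51, identical to the single model. The difference comes from the residual variance and df (41 versus 21), and 6.10 has already chosen the joint model. The 80.00–125.00% range appears only in the sample-size section. 6.10 assesses comparability from the ratios and intervals without a limit.

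It can also be argued that the 30% extrapolation rule creates the conflict even for completers. That requires reading evaluability parameter by parameter. 6.1.2 defines membership by period, so a dropped AUCinf can equally be an ordinary missing value in a model whose population is unchanged.

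The inconsistent label looks editorial. The addendum retitled Table 14.1.2.2 from PK Population to PK Evaluation Population, which suggests the terms are synonyms and that Tables 14.4.3 to 14.4.5 were missed.

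What stands is narrow: for a subject with two evaluable periods, the SAP text does not name the model's data set.

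**Conclusion.** No change to the plan follows. The singular heading of 6.1.2, its use as one label in SAP 6.4 and the ANOVA outputs, and the explicit single model in 6.10 point to one workable reading: fit the model to all evaluable periods of subjects who belong to at least one pair set, with the pair definitions showing who supports each contrast directly. An experienced analyst would do this unprompted. SAP 6.1 and Listing 16.2.3.1 show who was excluded, Listing 16.2.6.4 prints the ANOVA output, and SAP 7 covers any departure in the CSR.

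Redefining the population as anyone with at least one evaluable period would go further than reconciling the sections: it would replace a stated two-period rule after lock, for no gain in the contrasts under fixed subject effects.

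At a 10% CV, the choice between the single model and the pair sets changes the CI factor by at most about 0.004 in the patterns examined, and typically moves the estimate by 0.3% to 0.8%. At an assumed 40% CV the changes are larger (up to 1.233 versus 1.253, and 3.2%), but the standard error grows in proportion. These sizes rest on fixed subject effects, the 10% read as within-subject, the assumed patterns, and periods lost for reasons unrelated to exposure. With every period evaluable, the three populations are the same set.

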6.11 Safety Analyses

The safety analyses will be presented by the treatment received for the Safety Population.

6.11.1 Adverse Events

All AEs will be coded by system organ class (SOC) and preferred term (PT) using the latest version of the Medical Dictionary for Regulatory Activities (MedDRA, version 24.1 or higher) and summarized by treatment and overall.

A treatment emergent adverse event (TEAE) is defined as:

- Any AE that has an onset on or after the first dose of study drug.
- Any pre-existing AE that has worsened in severity on or after the first dose of study drug.

The following rules will be used to assign a TEAE to a treatment group:

- A TEAE will be assigned to the treatment received immediately before onset.
- Any TEAE reported within the washout period between doses will be attributed to the previous treatment.
- Any TEAE continued to multiple periods will be attributed to the period where it is started.

A treatment-related AE is defined as an AE as being possibly, probably or definitely related to the study drug. If an AE has missing relationship it is assumed to be related to the study drug for analysis purposes.

Maximum severity will be assumed for an AE with missing severity.

The following tables will be presented for AEs:

- Overall incidence and the number of TEAEs, Related TEAEs, Serious TEAEs, Serious Related TEAEs, Severity and Relationship to IMP.
- TEAE by system organ class and preferred term, incidence, and number of events.
- Treatment related TEAE by system organ class and preferred term, incidence, and number of events.
- Serious TEAE by system organ class and preferred term, incidence, and number of events.

QMD Ref: Worldwide-TMP-ST-006-4.0 Effective: 12Aug2019	Governing QMD: Worldwide-SOP-ST-001
Confidentiality Statement	

This document is the property of Worldwide Clinical Trials Inc. and may not be duplicated, copied, altered or removed from company without prior approval from Worldwide Quality Assurance or in compliance with Worldwide Standard Operating Procedures.

Worldwide Clinical Trials Controlled Quality Management Document		
 WORLDWIDE CLINICAL TRIALS	Sponsor:	Opiant Pharmaceuticals
	Protocol Number:	OPNT003-PK-002

- Treatment related serious TEAE by system organ class and preferred term, incidence, and number of events.
- TEAE leading to early withdrawal by system organ class and preferred term, incidence
- TEAE by system organ class, preferred term and maximum severity, incidence. If a subject had multiple occurrences of the same PT within a treatment period, it is counted once with maximum severity under the PT; if a subject had multiple PTs within the SOC with different grades of maximum severity, it is counted once within each applicable severity grade within the SOC and Any TEAE categories.
- TEAE by system organ class, preferred term and closest relationship, incidence. If a subject had multiple occurrences of the same PT within a treatment period, it is counted once with closest relationship under the PT; if a subject had multiple PTs within the SOC with different grades of closest relationship, it is counted once within each applicable relationship category within the SOC and Any TEAE categories. Listing of Serious TEAEs (presented in the Table section of the appendices).
- Listing of Deaths (presented in the Table section of the appendices).
- Listing of Adverse events leading to Early Withdrawal (presented in the Table section of the appendices).

All AEs will be separately listed.

In Mock Shells: Tables 14.3.1.1 to 14.3.1.8, Tables 14.3.2.1 to 14.3.2.3, Listing 16.2.7.1

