14.3.1.2	Adverse Events, Treatment Emergent Adverse Events by SOC and PT – Safety Population	IP	-
14.3.1.3	Adverse Events, Related Treatment Emergent Adverse Events by SOC and PT – Safety Population	IP	14.3.1.2
14.3.1.4	Adverse Events, Serious Treatment Emergent Adverse Events by SOC and PT – Safety Population	IP	14.3.1.2
14.3.1.5	Adverse Events, Related Serious Treatment Emergent Adverse Events by SOC and PT – Safety Population	IP	14.3.1.2
14.3.1.6	Adverse Events, Treatment Emergent Adverse Events leading to Early Withdrawal by SOC and PT – Safety Population	IP	14.3.1.2
14.3.1.7	Adverse Events, Treatment Emergent Adverse Events by SOC, PT and Maximum Severity - Safety Population	IP	-
14.3.1.8	Adverse Events, Treatment Emergent Adverse Events by SOC, PT and Closest Relationship - Safety Population	IP	-
14.3.2	Listings of Deaths, Other Serious and Significant Adverse Events		
14.3.2.1	Serious Adverse Event Data – Safety Population	IP	16.2.7.1
14.3.2.2	Adverse Event Leading to Death – Safety Population	IP	16.2.7.1
14.3.2.3	Adverse Event Leading to Early Withdrawal – Safety Population	IP	16.2.7.1
14.3.3	Narratives of Deaths, Other Serious and Certain Other Significant Adverse Events		

QMD Ref: Worldwide-TMP-ST-008-2.0 Effective: 12Aug2019	Governing QMD: Worldwide-SOP-ST-001
Confidentiality Statement	

This document is the property of Worldwide Clinical Trials Inc. and may not be duplicated, copied, altered or removed from company without prior approval from Worldwide Quality Assurance or in compliance with Worldwide Standard Operating Procedures.

Worldwide Clinical Trials Controlled Quality Management Document			
 WORLDWIDE CLINICAL TRIALS	Sponsor:	Opiant Pharmaceuticals	
	Protocol Number:	OPNT003-PK-002	
POST DATABASE LOCK STATISTICAL ANALYSIS PLAN ADDENDUM			

Table Number	Table Title	Validation Method	Shell Number (if repeat)
14.3.4	Abnormal Laboratory Values		
14.3.4.1	Hematology Data, Descriptive Statistics - Safety Population	IP	-
14.3.4.2	Clinical Chemistry Data, Descriptive Statistics - Safety Population	IP	14.3.4.1
14.3.4.3	Coagulation Data, Descriptive Statistics - Safety Population	IP	14.3.4.1
14.3.4.4	Urinalysis Data, Descriptive Statistics - Safety Population	IP	14.3.4.1
14.3.4.5	Hematology Data, Shift Summary - Safety Population	IP	-
14.3.4.6	Clinical Chemistry Data, Shift Summary - Safety Population	IP	14.3.4.5
14.3.4.7	Coagulation Data, Shift Summary - Safety Population	IP	14.3.4.5

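### In the maximum-severity and closest-relationship AE tables, the SOC and Any-TEAE rows count a subject in every applicable category, so they do not match the table titles or the PT rule and can overstate the lower categories

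*SAP*

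**What the plan says.** SAP section 6.11.1 lists the AE tables. The severity table is described as "TEAE by system organ class, preferred term and maximum severity, incidence". Its rule has two parts:

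- PT level: "If a subject had multiple occurrences of the same PT within a treatment period, it is counted once with maximum severity under the PT".
- SOC and Any-TEAE level: "if a subject had multiple PTs within the SOC with different grades of maximum severity, it is counted once within each applicable severity grade", and the sentence applies this to both of those levels.

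The relationship table is built the same way. A subject is counted once per PT at the closest relationship, and then, across PTs with differing relationships, "it is counted once within each applicable relationship category within the SOC and Any TEAE categories".

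The post-lock addendum keeps the titles. Table 14.3.1.7 is still "Adverse Events, Treatment Emergent Adverse Events by SOC, PT and Maximum Severity - Safety Population", and Table 14.3.1.8 still carries Closest Relationship. The addendum removes the Unknown row from the relationship category in Tables 14.3.1.1 and 14.3.1.8 but does not touch the counting rule.

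Three other statements in 6.11.1 bear on the point. AEs are "summarized by treatment and overall". Table 14.3.1.1 also reports "Overall incidence and the number of TEAEs, Related TEAEs, Serious TEAEs, Serious Related TEAEs, Severity and Relationship to IMP". And "All AEs will be separately listed".

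**The concern.** A subject has one maximum severity within an SOC and one across all TEAEs. A subject with a mild PT and a moderate PT in the same SOC has a maximum of moderate, yet the rule also enters that subject in the mild row. Within one table, the PT rows then follow the title and the SOC and Any-TEAE rows do not.

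Safety and tolerability is the secondary objective, and these are the two tables planned to show severity and relationship by SOC and PT. A reader who takes the higher-level rows at their title will read the mild row as subjects whose worst event was mild. The rows also cannot be checked by adding them up to the number of subjects with a TEAE.

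Two points are left open. The rule is triggered by several PTs inside one SOC but is applied to Any TEAE as well, so it does not say what happens at Any-TEAE level when the PTs lie in different SOCs. And the PT rule is worded per treatment period, so the Overall column of this crossover has no stated rule for a PT that recurs at different grades under different treatments.

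**Working it through.** The plan gives no figure to reproduce. The check applies the SAP rule and the once-per-level rule to the same data.

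**Inputs.** N = 24 (SAP section 4), taken as the denominator per treatment. The documents give no AE rates, grade mix or SOC spread, so everything else below is assumed.

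**Smallest case.** One subject, one mild and one moderate PT in one SOC, one treatment.
- SAP rule: mild 1 + moderate 1 = 2 entries for 1 subject.
- Once at the worst grade: moderate 1.
- Excess: 1/24 = 4.2 points, all in the mild row.
- If the subject has only one PT, however often it occurs, the two rules agree.

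**Assumed SOC.** Ten of 24 subjects have a TEAE: 5 mild only, 1 moderate only, 4 with one mild and one moderate PT.

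| Row | SAP rule | Once, at worst grade |
|---|---|---|
| Mild | 5 + 4 = 9 (37.5%) | 5 (20.8%) |
| Moderate | 1 + 4 = 5 (20.8%) | 1 + 4 = 5 (20.8%) |
| Sum | 14 | 10 |

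The top row is unchanged and the lower row is 4/24 = 16.7 points too high. With no mixed subjects the excess is zero.

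**Any-TEAE level.** Assume a Poisson number of distinct PTs per subject-period with mean m = 0.4 or 0.8, and grades mild/moderate/severe in proportions p = 0.75/0.20/0.05. Subjects with a TEAE: 24 × (1 − e^(−m)) = 7.9 or 13.2.

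*Broad reading:* every grade a subject has in any SOC is counted. Excess = 24 × [Σ(1 − e^(−m·p)) − (1 − e^(−m))].
- m = 0.4: 24 × [(0.2592 + 0.0769 + 0.0198) − 0.3297] = 0.63.
- m = 0.8: 24 × [(0.4512 + 0.1479 + 0.0392) − 0.5507] = 2.10.

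*Narrow reading:* a subject is counted at the overall worst grade, plus every grade in any SOC that holds more than one grade. Assume PTs spread evenly over K = 4 SOCs. Simulation of 400,000 subject-periods per scenario gives 0.18 (m = 0.4) and 0.70 (m = 0.8). Most of this is the mild row, which has a closed form: excess = 24 × [1 − (1 − q)^4], with q = (1 − e^(−0.75m/4)) × (1 − e^(−0.25m/4)).
- m = 0.4: q = 0.07226 × 0.02469 = 0.001784; excess 0.17.
- m = 0.8: q = 0.13929 × 0.04877 = 0.006793; excess 0.65.

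The small remainder is in the moderate row. The severe row is identical under both rules.

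**Milder grade mixes, narrow reading, m = 0.4 and 0.8.** 90/9/1%: 0.08 and 0.32. 95/5/0%: 0.04 and 0.16.

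**A single SOC row** (75/20/5%, K = 4). Total entries divided by subjects with a TEAE in that SOC = Σ(1 − e^(−m·p/4)) / (1 − e^(−m/4)) = 1.020 and 1.040.

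Only severity was worked through. Table 14.3.1.8 has the same structure, but nothing in the documents supports a particular mix of relationship categories.

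**The case against.** The strongest reply is that the rule is a disclosed convention. It stands in the same bullet as the table description, and it treats maximum severity as a property of each PT. An SOC row is then the union of the PT rows beneath it, which is coherent and reproducible. That stands: a reader might infer that the SAP contradicts itself or hides an error, and the text does not support either. What remains is that the titles, and the once-per-PT rule, lead a reader to expect something else from the higher rows.

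Second, the mock shells are not among the documents, and the addendum shows that they carry definitional footnotes. A footnote saying that subjects may appear in more than one category would largely remove the risk of misreading. This also stands: no such footnote is specified in the SAP or the addendum, but its absence from the shells cannot be shown.

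Third, the Any-TEAE figures depend on which reading is taken, on the number of SOCs and on assumed rates. This is correct and is why both readings are given. It is also part of the point, since two programmers could produce different Any-TEAE rows from the same text.

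Fourth, a reader might infer that severe, related or serious events are misreported. They are not. The rule only adds entries to lower categories; it cannot remove a subject from the highest one. The separate TEAE, related and serious tables do not use it.

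**Conclusion.** The point holds as a mismatch between the counting rule on one side and the table titles and PT-level rule on the other. At SOC and Any-TEAE level, Tables 14.3.1.7 and 14.3.1.8 will not show each subject's maximum severity or closest relationship. Their categories overlap, and any error runs one way, towards too many subjects in the less severe or less related rows.

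The size cannot be known from the documents and is zero if no subject has PTs of differing category. On the assumptions above, the Any-TEAE excess runs from under one to about two counts per 24, and a larger figure would need higher event rates than there is any basis for here. PT rows per treatment, the highest category, serious counts, the listings and every PK result are unaffected. Priority is minor: descriptive safety tables only.

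**What to change.** Amend the rule for Tables 14.3.1.7 and 14.3.1.8. Within each treatment, count each subject once at each level (PT, SOC, Any TEAE), at the highest severity or closest relationship across all that subject's TEAEs in that level. Apply the same rule across periods in the Overall column. Then check that the Any-TEAE rows agree with the severity and relationship rows of Table 14.3.1.1.

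If the sponsor prefers its present rule, the minimum is to retitle the two tables, footnote that a subject may appear in more than one category, and state how PTs in different SOCs are counted under Any TEAE.

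The cost is SAP wording, a small change to two table programs and one consistency check, with no new data. Because the existing addendum already postdates database lock, the change should be recorded as post-lock and explained in the CSR, as SAP section 7 provides.
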